Energy Expenditure	Ability to walk ¹¹	Patient questionnaire #4 and ability to complete gait speed test at time of assessment	Positive: Needing assistance with walking or being unable to walk Negative: No assistance needed for walking ¹¹
Gait speed	NIH 4 meter gait speed test ^{24,25}	Administered by research assistant or trained caregiver	Positive: Rapid gait speed less than or equal to cut-points provided by Gill et al. ²⁶ Negative: Rapid gait speed greater than cut-points provided by Gill et al. ²⁶

Grip strength	Jamar Hand Dynamometer (Sammons Preston Roylan, Bolingbrook, IL) grip strength test ²⁶	Administered by research assistant or estimated by the following question: Do you have difficulty gripping with your hands (e.g. opening a jar)? Yes or No.	Positive: Average strength less than or equal to the cut-points provided by Fried et al., ³ or self-reported difficulty gripping Negative: Average strength greater than the cut-points provided by Fried et al., ³ or no self-reported difficulty gripping
----------------------	---	---	--

We will calculate two scores for frailty; one based on the cumulative deficit model and the other on the phenotype model. If patient's score as frail or pre-frail by either method they will be eligible for evaluation by a geriatrician.

For the Cumulative deficit score (table 1), the cumulative total of deficits is determined by adding all of the deficits that are present (deficit present = 1, deficit absent = 0, and for some variables, partial deficit = 0.25, 0.5, or 0.75) and dividing the result by the total number of items in the index. This study will use a frailty index comprising of 43 items (see appendix A). Of note, up to 92 symptoms can be assessed, although as few as 30 items can be used without loss of predictive validity.^{18,20} Furthermore, the actual composition of the index is not crucial. As long as a sufficient number of variables are used, the variables can be selected at random and still yield comparable results.²⁷ After calculating a total frailty score on the 0-1 scale, cut-points of 0-0.2 for "robust", 0.2-0.35 for "pre-frail", and 0.35-1.0 for "frail" will be used to categorize patients, as was done in the Sheppard study.¹⁶

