5.4 Data Collection Procedures

Patients will be approached or contacted by the research assistant either at their scheduled appointment with the DFCI oncologist (in-person) or shortly after that appointment (virtual). The research assistant will then consent the patients and document consent with either the patient's wet-ink signature (in-person) or the signature of the research assistant verifying that verbal consent was given (virtual). The assessment will be conducted in-person or remotely, by phone or video conference, to preserve the safety of our patient population during the ongoing COVID-19 pandemic.

In-person assessments will begin with a 28-item self-report questionnaire (see appendix B) filled out by the patient. Next, the research assistant will administer the delayed recall section of the Montreal Cognitive Assessment (MoCA), clock-in-the-box test, grip strength test, and gait speed test. That will end the in-person frailty assessment. Virtual assessments contain minor changes to accommodate remote completion. The 28-item questionnaire, MoCA recall, and modified Clock Draw are conducted by the research assistant during a telehealth appointment. A patient caregiver will be trained to administer a remote gait speed test with a 4-meter strip of

ribbon that will be mailed in advance. Grip strength will be estimated using the following question: *“Do you have difficulty gripping with your hands (e.g. opening a jar)? Yes or No.”*

At baseline, the research assistant will perform a medical record review to obtain comorbidity information and body mass index. A follow up medical record review will be completed at one year from enrollment in order to obtain the outcome data listed in Table 3, which are all secondary outcomes of interest. There will also be general periodic assessments for overall survival.

Table 3: Summary of outcomes

Outcome:	Timeline for assessment:	Operationalization	Obtained from:
Survival*	6 months, 1 year	Overall survival	Patient medical record and outside records
Disease severity	Baseline	Disease Severity	Patient medical record and outside records
Treatment assignment	6 months	Supportive care only vs. chemotherapy vs. low dose chemotherapy vs. investigational treatment; any disease-modifying treatment versus not	Patient medical record and outside records
Hospitalizations	6 months	Number and length of hospitalizations since enrollment	Patient medical record and outside records

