	31 CHF	
	32 Stroke	
	33 Cancer	
	34 Diabetes	
	35 Arthritis	
	36 Chronic Lung Disease	

Assessed by research staff	37	BMI	See Tables below for cut points
	38	*Usual pace walk speed	
	39	*Rapid pace walk speed	
	40	MoCA 5 word delayed recall	
	41	*** Clock-in-the-box or Clock Draw	
	42	Ability to explain presentation to DFCI	
	43	Ability to complete assessment without assistance of others	“Yes” = 0; “No” = 1

* Also used in calculation of Phenotype Frailty Score

** Used in calculation of Phenotype Frailty Score if respective physical measure is not available

*** Clock-in-the-box used during in-person assessments; Clock Draw used during virtual assessments

Physical variable cut-points¹²

Variable	Deficit for Men	Deficit for Women	Source of Cut point
Body Mass Index (BMI)	<18.5, \geq 30 as a deficit. 25-<30 as a 'half deficit'	<18.5, \geq 30 as a deficit. 25-<30 as a 'half deficit'	Published ²⁹
Grip Strength (GS in kg)	For BMI \leq 24, GS \leq 29 For BMI 24.1–28, GS \leq 30 For BMI >28, GS \leq 32	For BMI \leq 23, GS \leq 17 For BMI 23.1–26, GS \leq 17.3 For BMI 26.1–29, GS \leq 18 For BMI >29, GS \leq 21	Published ^{3,26}
Rapid pace Walk	<0.61 m/s (6.56 sec)	<0.61 m/s (6.56 sec)	Published ²⁶
Usual pace Walk	<0.38 m/s (10.50 sec)	<0.38 m/s (10.50 sec)	Published ¹²

MoCA 5 word delayed recall normative data and cut-points¹⁴

Memory	Normal Control		Mild Cognitive Impairment		Alzheimer's Disease	
	AVG	SD	AVG	SD	AVG	SD
	3.73	1.27	1.17	1.47	0.52	1.03
Words Recalled Successfully	5	4	3	2	1	0
Corresponding CDM Score	0	0.25	0.5	0.75	1	1

Clock-in-the-box (CIB) normative data for age and education and cut-points²²

Age (y)	Education			
	Less than High School (SD)	High School (SD)	College (SD)	Graduate School (SD)
75-79	5.1 (1.9)	6.3 (1.6)	6.4 (1.3)	6.6 (1.4)
80-84	4.6 (1.9)	5.8 (1.5)	5.9 (1.6)	6.7 (1.2)

>85	4.9 (1.3)	5.4 (1.3)	5.8 (1.7)	6.5 (1.5)	
CIB Score	8	7	6	5	0-4
Clock Draw Score	7	6	5	4	0-3
Corresponding CDM Score	0	0.25	0.5	0.75	1

Phenotype Model Variable Index

	Index Item*	Measured Variable	Scoring
1	21	Weight loss	Yes=1, No=0
2	24,25	Self-Reported Exhaustion	Most of the time (for either) =1, some or rarely (for both) =0
3	4	Energy Expenditure	Some assistance or completely unable=1, without assistance=0
4	38,39 or 23	Gait Speed (usual and rapid pace)	IF 38, 39: Slower than cut-point=1, faster than cut-point=0 IF 23: “Slow” = 1; “Steady Average” or “Fast” = 0

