Appendix B: Patient Questionnaire

The following items (1-14) are about activities you might do during a typical day. Are you able to do these activities- Without help? With Some Help? or Completely Unable?

(Please Circle One Number on Each Line)

	Without help	With Some Help	Completely Unable					
1. Taking a bath or shower	[1]	[2]	[3]					
2. Getting Dressed	[1]	[2]	[3]					
3. Getting in/out of a chair	[1]	[2]	[3]					
4. Walking around the house	[1]	[2]	[3]					
5. Eating	[1]	[2]	[3]					
6. Grooming (personal hygiene)	[1]	[2]	[3]					
7. Using the toilet	[1]	[2]	[3]					
8. Going up/down stairs	[1]	[2]	[3]					
9. Lifting 10 lbs	[1]	[2]	[3]					
10. Shopping	[1]	[2]	[3]					
11. Doing housework	[1]	[2]	[3]					
12. Preparing meals	[1]	[2]	[3]					
13. Taking medication	[1]	[2]	[3]					
14. Handling your own money	[1]	[2]	[3]					
15. During the last week, on how many days did you walk outside? (circle one)	0	1	2	3	4	5	6	7

16. Which option below describes your level of physical activity over the past week? (mark one)

- Fully active, able to carry on all usual activities without restriction

- Restricted in strenuous activity; can walk; able to carry out light housework
- Can walk and care for self; up more than 1/2 day
- Need some help taking care of self; spend more than 1/2 day in bed or chair
- Cannot take care of self at all and spend all of my time in bed or chair

17. Overall, how would you rate your health? (circle one)

Excellent Very good Good Fair Poor

18. How would you say your health has changed in the last year? (mark one)

Worse Same Better

19. In the last month, have you ever stayed in bed at least half of the day due to your health?

Yes No

20. In the last month, have you cut down on your usual activity due to your health?

Yes No

21. Have you lost more than 10 lbs unintentionally in the last year?

Yes No

22. Do you have difficulty gripping with your hands (e.g. opening a jar)?

Yes No

23. Which of the following best describes your usual walking pace?

Slow Steady Average Fast

24. How often do you feel that everything is an effort?

Most of the time Some of the time Rarely

25. How often do you feel that you have trouble getting going?

Most of the time Some of the time Rarely

26. How often do you feel depressed?

Most of the time Some of the time Rarely

27. How often do you feel lonely?

Most of the time Some of the time Rarely

28. How often do you feel happy?

Most of the time Some of the time Rarely

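### Appendix A replaces an unavailable gait or grip test by self-report whatever the reason, so physical inability can score as no deficit, and its energy expenditure row conflicts with Table 2

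*Combined protocol and SAP*

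**What the plan says.** The phenotype score has five criteria. None positive is robust, one or two is pre-frail, three or more is frail (Section 5.3).

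- **Fallback.** In Appendix A, item 22 (difficulty gripping) and item 23 (self-reported walking speed) carry the footnote "Used in calculation of Phenotype Frailty Score if respective physical measure is not available". No reason for the missing measure is asked for.
- **Gait row, Appendix A.** For the measured test: "IF 38, 39: Slower than cut-point=1, faster than cut-point=0". Otherwise item 23 is used, with *Slow* scored 1 and *Steady Average* or *Fast* scored 0. The row has no code for a test that could not be completed.
- **Question 23, Appendix B.** It asks "Which of the following best describes your usual walking pace" and offers those three paces only.
- **Grip row, Appendix A.** If the fallback is used, *Yes* to question 22 scores 1 and *No* scores 0.
- **Energy expenditure, Table 2.** The inputs are "Patient questionnaire #4 and ability to complete gait speed test at time of assessment", and the rule is "Positive: Needing assistance with walking or being unable to walk".
- **Energy expenditure, Appendix A.** The row cites item 4 (walking around the house) alone: "Some assistance or completely unable=1, without assistance=0".
- **How the tests are given.** Table 2 lists gait as "Administered by research assistant or trained caregiver", with no self-report alternative. For virtual visits, Section 5.4 has a caregiver run the walk, whereas for grip "Grip strength will be estimated using the following question".

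**The concern.** A missing performance test can mean two different things. It may not have been given, because the visit was virtual or no caregiver was at hand. Or the patient may have tried and failed, or been physically unable to try. In the first case self-report is a reasonable substitute. In the second, the failure is itself evidence of the deficit, and Appendix A discards it. A patient who finishes the walk slowly scores 1 on gait, while one who cannot finish it may score 0.

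The protocol treats inability as a deficit elsewhere: items 1 to 14 offer *Completely Unable* as an answer and score it 1. Table 2 does the same with the walk, under energy expenditure, but that input does not appear in the scoring table.

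What is at stake is the line between robust and pre-frail. Section 6.1 plans to compare frail and pre-frail together against robust in Aim 1, and Section 5.1 has the same two-way status emailed to clinicians. The study also sets out to validate the phenotype approach in its own right (Section 2.2).

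**Working it through.** The plan states no figure to reproduce. The check scores one patient under each rule.

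**Gait.** Take a patient who cannot complete the 4-metre walk, answers *without help* to item 4, and answers *Steady Average* or *Fast* to question 23. Let *k* be the number of positives among weight loss, exhaustion and grip (0 to 3).

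- Rule A, Appendix A as written: energy 0, gait 0, total *k*.
- Rule B, Table 2 (failed test counts under energy): energy 1, gait 0, total *k* + 1.
- Rule C, inability counts under gait only: energy 0, gait 1, total *k* + 1.
- Rule D, inability counts under both: energy 1, gait 1, total *k* + 2.

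| *k* | Rule A | Rule B or C | Rule D |
|---|---|---|---|
| 0 | 0, robust | 1, pre-frail | 2, pre-frail |
| 1 | 1, pre-frail | 2, pre-frail | 3, frail |
| 2 | 2, pre-frail | 3, frail | 4, frail |
| 3 | 3, frail | 4, frail | 5, frail |

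A and B are both current text. They give different categories at *k* = 0 (robust against pre-frail) and at *k* = 2 (pre-frail against frail). B and D differ in category only at *k* = 1, so it also matters whether one failed walk counts once or twice.

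If item 4 is answered *with some help* or *completely unable*, Appendix A already scores energy as 1. The patient is then at least pre-frail, and only pre-frail against frail can change.

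**Grip.** Take a patient who cannot do the dynamometer test and answers *No* to question 22. Let *m* be the positives among the other four criteria. The total is *m* under Appendix A and *m* + 1 if inability counts.

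| *m* | Appendix A | Inability scored 1 |
|---|---|---|
| 0 | robust | pre-frail |
| 1 | pre-frail | pre-frail |
| 2 | pre-frail | frail |
| 3 or 4 | frail | frail |

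No other criterion takes grip failure as an input, so nothing offsets the error at *m* = 0.

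**Effect on the analysis.** A shift between robust and pre-frail moves a patient across the pooled Aim 1 contrast. A shift between pre-frail and frail affects, within Aim 1, only the three-group comparison, which Section 6.1 makes conditional on power.

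**Is a missing gait test just the virtual mode?** No. Section 5.4 keeps a caregiver-run walk in virtual visits, so missing gait data can mix logistics with inability. For grip, self-report is the planned virtual measure. Unless the reason is recorded, an in-person failure is handled in the same way as a virtual visit.

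**The case against.** The strongest reply is that Table 2 already handles gait. Under it, a patient who fails the walk is positive on energy expenditure and so at least pre-frail; item 4 in Appendix A catches many others. This stands. The fall to robust on gait requires Appendix A to be applied as written, without Table 2's second input. But Appendix A is the scoring table, and nothing says which of the two governs.

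The error also requires a favourable self-report from someone who could not do the test. For grip, that means denying difficulty gripping, which is probably uncommon. This stands too, and it limits the size.

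The cumulative deficit score is a second route to geriatrician eligibility (Section 5.3). It is no sure backstop: the pre-frail threshold of 0.2 on 43 items needs 0.2 × 43 = 8.6 deficits. It also does not help where the phenotype is validated on its own.

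A reader might infer three stronger things that the documents do not support:

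- *A blank on question 23 scores 0.* Appendix A gives 0 only to two named answers and states no score for a blank. That is a gap, not a rule.
- *The sickest patients are moved down.* A move to robust requires every other criterion to be negative, which is not the profile of the sickest. A weaker frailty-survival association is plausible but not shown.
- *A count of affected patients can be given.* If one assumed that 3% to 8% of the 1,620 hoped-for patients cannot do the walk and that 20% to 40% of those do not answer *Slow*, the product would be about 10 to 52 (1,620 × 0.03 × 0.20 to 1,620 × 0.08 × 0.40). Neither share is in the documents. The product also counts patients one criterion too low, not patients whose category changes.

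**Conclusion.** The concern holds in a narrow form and should be fixed. The fallback in Appendix A is a stated rule that can score physical inability as no deficit on gait or grip. On gait it combines with a contradiction: Table 2 uses completion of the walk for energy expenditure and Appendix A does not, so one patient can be robust by one table and pre-frail by the other. On grip there is no second criterion to catch the failure.

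The size is one criterion out of five. When inability is counted once, the category changes only if the other four criteria total 0 or 2, and the pooled Aim 1 contrast is touched only at 0. The number of such patients is probably small and cannot be derived from the documents. The conclusion rests on reading *not available* as covering a failed test, which the wording allows and nothing excludes, and on reading Table 2's completion input as making a failed walk positive. It concerns the phenotype score only.

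**What to change.** 1. In Appendix A, limit the item 22 and 23 fallback to tests not administered for logistic reasons. Where the patient tried and could not complete the test, or could not try for physical reasons, score the criterion as present.
2. Reconcile the energy expenditure row of Appendix A with Table 2, and state whether one failed walk counts under one criterion or both. The choice decides pre-frail against frail when exactly one of weight loss, exhaustion and grip is positive.
3. State how a blank on question 22 or 23 is handled.
4. Add a reason code for each missing gait or grip test: not administered, attempted and not completed, or not attempted because physically unable.
5. Where no reason was recorded, run the pooled Aim 1 contrast both ways, with the missing test scored by self-report and with it scored as present, and report both.
6. In the same edit, correct the index number in the grip row. It points to item 36, which is chronic lung disease; the 43-item list has no measured grip item.

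The cost is a few scoring lines, one field on the assessment form and one sensitivity analysis. The reason may not be recoverable for patients already assessed, which is why step 5 is needed.

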Appendix B: Patient Questionnaire

The following items (1-14) are about activities you might do during a typical day. Are you able to do these activities- Without help? With Some Help? or Completely Unable?

(Please Circle One Number on Each Line)

	Without help	With Some Help	Completely Unable					
1. Taking a bath or shower	[1]	[2]	[3]					
2. Getting Dressed	[1]	[2]	[3]					
3. Getting in/out of a chair	[1]	[2]	[3]					
4. Walking around the house	[1]	[2]	[3]					
5. Eating	[1]	[2]	[3]					
6. Grooming (personal hygiene)	[1]	[2]	[3]					
7. Using the toilet	[1]	[2]	[3]					
8. Going up/down stairs	[1]	[2]	[3]					
9. Lifting 10 lbs	[1]	[2]	[3]					
10. Shopping	[1]	[2]	[3]					
11. Doing housework	[1]	[2]	[3]					
12. Preparing meals	[1]	[2]	[3]					
13. Taking medication	[1]	[2]	[3]					
14. Handling your own money	[1]	[2]	[3]					
15. During the last week, on how many days did you walk outside? (circle one)	0	1	2	3	4	5	6	7

16. Which option below describes your level of physical activity over the past week? (mark one)

- Fully active, able to carry on all usual activities without restriction

- Restricted in strenuous activity; can walk; able to carry out light housework
- Can walk and care for self; up more than 1/2 day
- Need some help taking care of self; spend more than 1/2 day in bed or chair
- Cannot take care of self at all and spend all of my time in bed or chair

17. Overall, how would you rate your health? (circle one)

Excellent Very good Good Fair Poor

18. How would you say your health has changed in the last year? (mark one)

Worse Same Better

19. In the last month, have you ever stayed in bed at least half of the day due to your health?

Yes No

20. In the last month, have you cut down on your usual activity due to your health?

Yes No

21. Have you lost more than 10 lbs unintentionally in the last year?

Yes No

22. Do you have difficulty gripping with your hands (e.g. opening a jar)?

Yes No

23. Which of the following best describes your usual walking pace?

Slow Steady Average Fast

24. How often do you feel that everything is an effort?

Most of the time Some of the time Rarely

25. How often do you feel that you have trouble getting going?

Most of the time Some of the time Rarely

26. How often do you feel depressed?

Most of the time Some of the time Rarely

27. How often do you feel lonely?

Most of the time Some of the time Rarely

28. How often do you feel happy?

Most of the time Some of the time Rarely
